A significant shift from baseline which can be attributable to the radiotracer injection and not the patient's medical condition will be considered an unexpected AE. **An event greater than 10 hours post scan will not be considered an AE since the radiotracer has effectively decayed by 10 hours.**

The National Cancer Institute's Common Terminology Criteria for Adverse Events (CTCAE) Version 4.03 (June 14, 2010) will be used as a guide address potential AEs subject to limitations above and medical and scientific judgment as to plausibility of such criteria in a diagnostic radiotracer study.

Adverse Event Reporting

An SAE is defined as any adverse event occurring at any dose that results in any of the following outcomes:

- death
- a life-threatening adverse experience
- inpatient hospitalization or prolongation of existing hospitalization
- a persistent or significant disability/incapacity

- a congenital anomaly/birth defect

Other important medical events may also be considered an SAE when, based on appropriate medical judgment, they jeopardize the subject or require intervention to prevent one of the outcomes listed. Any serious adverse events (see above) will be communicated by the PI to the Emory IRB using standard adverse event reporting forms. In case of a serious adverse event definitively ascribed to 68Ga-DOTATATE imaging, Drs. [name], [name], and [name], will meet formally or communicate via email to investigate the reported adverse event.

The Investigator will report all Serious Adverse Events (as defined above) occurring in a subject on the day of or within 28 days following the Agent administration to Pharsafer® Associates Ltd (“**Pharsafer**”) by telephone ([name]), FAX ([name]) or e mail ([contact]). Events should be reported to Pharsafer within 24 hours of the investigator becoming aware of the events occurrence. The Investigator is responsible for informing the ethics committee of serious events occurring during the study in compliance with local regulations.

Any patient death that may be due to the study procedure (i.e. severe radiotracer reaction), unanticipated problem, would be promptly reported to the Emory IRB office. Additionally any patient death not associated with the study procedure or serious unanticipated event(s) (i.e. radiotracer allergy) will be reported to the Emory IRB and FDA upon continuing review. Protocol deviation/non-compliance will be reported according to IRB Policies & Procedures.

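### Section F's 10-hour AE cut-off conflicts with its own 28-day SAE rule and with Section G, so a late serious tracer reaction can miss the main reporting routes

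*Combined protocol and SAP*

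**What the plan says.** All of this is in the combined protocol and SAP.

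- **AE definition (Section F).** The opening definition is broad. It has no time limit and applies whatever the relation to the drug. A bold sentence then narrows it: "An event greater than 10 hours post scan will not be considered an AE since the radiotracer has effectively decayed by 10 hours". Serious events are not excepted.
- **SAE definition (Section F, Adverse Event Reporting).** "An SAE is defined as any adverse event occurring at any dose that results in any of the following outcomes", followed by the usual list from death to birth defect. A discretionary clause follows: "Other important medical events may also be considered an SAE when, based on appropriate medical judgment", the subject is put at risk or needs treatment to avert a listed outcome.
- **Routes that use the term SAE.** For the IRB: "Any serious adverse events (see above) will be communicated by the PI to the Emory IRB using standard adverse event reporting forms". For the safety contractor, the investigator is to "report all Serious Adverse Events (as defined above) occurring in a subject on the day of or within 28 days following the Agent administration", and to do so "within 24 hours of the investigator becoming aware of the events occurrence". For the study doctors' review: "In case of a serious adverse event definitively ascribed to 68Ga-DOTATATE imaging", they meet or correspond by e-mail to investigate.
- **Routes that do not use the term.** "The Investigator is responsible for informing the ethics committee of serious events occurring during the study in compliance with local regulations". A death that may be due to the procedure goes promptly to the IRB. That sentence also contains the words 'unanticipated problem', without saying whether they are a separate trigger. Deaths not associated with the procedure, and serious unanticipated events (radiotracer allergy is the example given), go to the IRB and FDA at continuing review.
- **Section G.** Its last sentence limits reporting to SAEs related to the tracer, because the therapy is not experimental. The sentence before it gives a median survival of 18 months and expects most SAEs to come from the disease or its treatment.

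**The concern.** The 10-hour sentence removes late events from the AE category, and an SAE has to be an AE. A 28-day SAE duty therefore sits on a definition that ends within hours of the scan. Section G adds a relatedness limit that the 28-day sentence does not have. A coordinator who learns on day 2 of an admission for an allergic reaction has three rules to choose from, and the choice decides whether the 24-hour clock starts.

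The reason given for the cut-off does not cover the events the protocol itself names. Decay bears on radiation. The examples in Sections F and G are radiotracer allergy, severe radiotracer reaction and IV-site problems. Section G gives patients telephone numbers for such problems with no time limit, so a patient may report something that Section F says is not an AE.

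The doctors' review has a second limit, which applies even inside 10 hours. Attribution must already be definite before the investigation that would establish it can start. For deaths, Section F uses the lower standard of an event that may be due to the procedure.

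**Working it through.** There is no plan figure to reproduce. The check traces the definitions, then does some simple arithmetic.

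**1. Trace one event through the text.** Take a serious, non-fatal allergic reaction that starts the day after the scan, and read Section F literally.

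| Route | Depends on the SAE term? | Result for this event |
|---|---|---|
| IRB SAE form | Yes, it points back to the definition | Not triggered |
| Contractor report, 24 hours, to day 28 | Yes, it points back to the definition | Not triggered |
| Study doctors' review | Yes, and attribution must be definite | Not triggered |
| Ethics-committee notice | No, it refers to serious events | Triggered, no time stated in the protocol |
| Prompt IRB report | No | Clear for deaths; unclear whether 'unanticipated problem' covers this event |
| IRB and FDA at continuing review | No | Triggered, but deferred |
| Important-medical-event clause | A possible way back in | Discretionary ('may') |

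The only route with a stated clock is one of the three that drop out.

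**2. Compare the windows.** Inputs: 28 days after administration and 10 hours post scan (Section F); about 120 minutes or less for the whole study including injection (Section C.2).

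- Contractor window: 28 × 24 = 672 h.
- Cut-off measured from injection: 10 + 0 = 10 h to 10 + 2 = 12 h.
- Share of the window in which an SAE can exist: 10/672 = 1.5% to 12/672 = 1.8%.
- Remainder: 98.2% to 98.5%.

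**3. How often might the rules collide?** Only deaths can be sized from the documents. Inputs: median survival 18 months (Section G); 20 patients (Section C). Assumption: constant hazard from the day of injection.

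- Median in days: 18 × 30.44 = 548. Daily hazard: ln 2/548 = 0.001265.
- Death by day 28: 1 − exp(−28 × 0.001265) = 3.48%.
- Death by 12 h: 1 − exp(−0.5 × 0.001265) = 0.063%.
- Between the two: 3.42% per patient, which gives 20 × 0.0342 = 0.68 expected deaths.
- At least one: 1 − (1 − 0.0342)^20 = 50%.

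| Hazard | Expected deaths, cut-off to day 28 | Chance of at least one |
|---|---|---|
| As from the 18-month median | 0.68 | 50% |
| Half | 0.34 | 29% |
| A quarter | 0.17 | 16% |

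The lower rows matter because Section B describes patients about to start first-line treatment for castration-resistant disease, typically with better performance status than patients further along. Hospitalisations would add to these counts, but the documents give no rate.

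**The case against.** **The literal reading is strained.** It makes a specific 28-day duty almost empty. The back-reference in the contractor sentence can be read as pointing only to the seriousness outcomes listed just above it, and a specific rule would ordinarily prevail over a general one. This has force, and many sites would probably report on the 28-day rule. But the 10-hour sentence is in bold and has no exception, the CTCAE sentence after it is made subject to the limitations above, and Section G points to a third rule. A safety duty should not depend on which sentence a coordinator gives precedence.

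**Other routes survive.** They do, and they limit the consequence. A reader might infer that a late serious event would go wholly unreported. The documents do not support that. Section G calls for tracer-related SAEs to be reported, although it too uses the SAE term. Deaths have IRB routes that do not depend on timing, and the ethics-committee and continuing-review wording remains. What is lost on the literal reading is the SAE form, the timed report and the doctors' review.

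**The numbers do not measure harm.** This is correct. A reader might take 98% or 50% as a risk to patients. The first is a ratio of window lengths. The second is the top of a range under an assumed hazard, and it counts deaths that would nearly all be due to the disease.

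**Silence on the DSMC.** Section F names the DSMC on no SAE route, but the committee's own procedures are not in the documents, so nothing follows from that.

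**Conclusion.** The conflict is real and should be removed. Sections F and G give three rules for serious events (10 hours, 28 days, tracer-related only) that cannot all be followed. On a literal reading, a late serious non-fatal tracer reaction loses the three routes meant for it and keeps only slower, discretionary or ambiguous ones. The 'definitively ascribed' threshold weakens the doctors' review at any time after injection.

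The conclusion rests on the wording alone. The death counts show only that the trial could well meet the conflict, and they depend on the constant-hazard assumption. Late serious tracer reactions may be rare. It would also go too far to infer that the trial's findings are at risk: this concerns safety reporting, and the imaging and progression analyses do not change.

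**What to change.** Three edits to existing sentences:

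1. **Section F, 10-hour sentence.** Keep the limit but confine it: 'A non-serious event that starts more than 10 hours after the scan is not counted as an AE. This limit does not apply to any event that meets an SAE outcome or the important-medical-event criterion below and occurs on the day of injection or within the next 28 days.' The limit must be restated in full, because this is the only place that defines it.
2. **Section F, study doctors' review.** Replace 'definitively ascribed to' with 'judged at least possibly related to', which matches the standard already used for deaths.
3. **Section G, last sentence.** 'All SAEs within 28 days are reported as in Section F; those at least possibly related to the tracer also go to the study doctors' review.'

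The SAE window then becomes the full 672 hours.

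**Cost.** No new visit, committee or type of form. There would be a few more IRB forms and contractor reports for disease-related serious events to day 28. Deaths account for about 0.2 to 0.7 in total on the assumptions above, plus hospitalisations at an unknown rate. The 28-day sentence already asks for the contractor reports; the IRB forms are the added work, and Section G's narrower policy is given up.

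**What it leaves.** Late non-serious tracer reactions stay excluded by timing. A hold on further injections, a deadline for the doctors' decision and a copy to the DSMC are options for the sponsor; none is needed to remove the conflict.

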The goal of our proposal is to determine the feasibility of identifying neuroendocrine transdifferentiation in NEPC patients using noninvasive imaging, and assess whether such an early imaging biomarker can predict eventual progression. Specifically we plan to employ the newly FDA approved PET radiotracer ⁶⁸Ga-DOTATATE as an off-label probe for somatostatin receptors that have been shown to be upregulated in prostate cancer when compared to somatostatin receptor expression in normal prostate tissue and in benign prostate hypertrophy (36, 37). This upregulation of somatostatin receptors in early castration resistance may explain in part the mechanism of neuroendocrine transdifferentiation (36, 38). While prostate cancer may be indolent, it can also be rapidly lethal in a subset of patients. Early identification of this progression could potentially be utilized in the future to study adaptive therapy strategies. In addition, NEPC is underdiagnosed as men rarely undergo biopsy of metastatic lesions after spread to soft tissue and bones which is required for histologic confirmation (2). Furthermore, standard biopsy is subject to sampling error both within a lesion itself and on a global basis, since all lesions cannot ethically undergo biopsy. Therefore, we will determine if global body interrogation via a noninvasive imaging method to probe for somatostatin receptor upregulation is feasible, and generate preliminary data to investigate the relationship of the degree of PET uptake with treatment outcome with

our ultimate goal to determine if uptake on an initial ⁶⁸Ga-DOTATATE PET can be used as an early predictive imaging biomarker of outcome.

Primary Objective. Establish the feasibility of using ⁶⁸Ga-DOTATATE PET as a predictive imaging biomarker for neuroendocrine transdifferentiation in prostate cancer.

Secondary Objective. Correlate progression of disease with degree of uptake on ⁶⁸Ga-DOTATATE PET examination.

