Radiochemistry staff will perform syntheses, conduct quality control tests and approve the final preparation following USP standards according to the NETSPOT prescribing information. The NETSPOT kit is supplied as 2 vials and an accessory cartridge which allows for direct preparation of Ga 68 DOTATATE injection with the eluate from an Eckert & Ziegler GalliaPharm Germanium 68/Gallium 68 (Ge 68/Ga 68) generator (Scheme 2). Ge 68 breakthrough and other gamma emitting radionuclides should be $\leq 0.001\%$. The Ga 68 chloride is sterile as eluted from the GalliaPharm generator. Vial 1 (reaction vial with lyophilized powder contains: 40 mcg dotatate, 5 mcg 1,10 phenanthroline; 6 mcg gentisic acid; 20 mg mannitol) is pierced with a sterile needle connected to a 0.22 micron sterile vented filter to maintain atmospheric pressure within the vial during the reconstitution process. Using a 1 mL sterile syringe, the required volume of the reaction buffer from Vial 2 (buffer vial contains: 60 mg formic acid; 56.5 mg sodium hydroxide and water for injection) is withdrawn. The generator is eluted directly into Vial 1 through the accessory cartridge (accessory cartridge contains: 660 mg porous silica. The accessory cartridge reduces the amount of Ge 68 potentially present in generator eluate) to reconstitute the lyophilized powder with 5 mL of eluate. The syringe and the 0.22 micron sterile air venting filter are removed from vial 1, and Vial 1 is moved to the heating hole of the dry bath, leaving the vial at 203 °F (95 °C, not to exceed 98 °C) for at least 7 minutes (not exceeding 10 minutes heating) without agitation or stirring. After 7 minutes, the vial from the dry bath is placed in an appropriate lead shield and let cool down to room temperature for approximately 10 minutes. After which, the appropriate quality controls are performed according to recommendations. The amount of radioactivity injected into the patient's IV is recorded immediately prior to injection, with residual activity in the syringe recorded immediately after injection. The single IV injection will contain a maximum mass dose of 68Ga-DOTATE of $\leq 50\ \mu\text{g}$. The total volume administered is typically between 2 and 20 mL with the recommended amount of radioactivity to be administered for PET imaging is 2 MBq/kg of body weight (0.054 mCi/kg) up to 200 MBq (5.4 mCi).

Scheme 2:

C.2 PET-CT imaging protocol

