G. Data and Safety Monitoring Plan (DSMP):

Patients will be monitored by the technologists and study nurse before and after whole body Ga-68 DOTATATE PET-CT examination for any adverse events/reactions per clinical routine. They will be given contact phone numbers to call if they experience any problems (i.e. problems with the IV site, any allergic reaction symptoms). They will be followed routinely by their referring oncologist with clinical exams, and the PI will work with the co-investigators and referring physicians to ensure that the patients continue to follow up as scheduled.

The Data and Safety Monitoring Committee (DSMC) of the Winship Cancer Institute will also oversee the conduct of this study (every 6 months or annually – depending on the risk level of the protocol). This committee will review pertinent aspects of study conduct including patient safety, compliance with protocol, data collection and efficacy. The committee will review the charts of 10% of patients enrolled to the study and two of the first 5 patients entered to the study. The Committee reserves the right to conduct additional audits if necessary. The Principal Investigator (PI) or designee is responsible for notifying the DSMC about the accrual of patients when the first 5 have been entered to the study.

It should be kept in mind that this patient cohort typically has a median survival of 18 months and it is of much greater probability that an SAE may occur and be related to the patient's natural disease progression and/or therapy. Only those SAE's related to the radiotracer Ga-68 DOTATATE itself will be reported as part of this trial as the therapy itself is not considered experimental.

H: Pharmaceutical, biologic, and device information

Radiation Dosimetry. The study will be approved by not only the Emory IRB but also the Radiation Safety Committee. The maximum number of PET studies a patient will receive in one year is 1 Ga-68 DOTATATE study.

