Depending on the distribution of the radionuclide in the body, the whole body dose may not be the critical factor in single or longitudinal studies. It is also of interest to know which organ receives the highest absorbed dose. This organ is referred to as the critical organ. Often the limit for an individual organ dose is reached before the limit established for the whole-body. The United States Food and Drug Administration in Title 21 CFR Part 361 limits the whole body radiation dose to adult research subjects to less than 3 rem (30 mSv) for a single injection and 5 rem (50 mSv) effective dose equivalent (EDE) annually. A single organ cannot receive more than 5 rem (50mSv) in a single injection and 15 rem (150 mSv) effective dose equivalent annually. These constraints on dose will limit the maximum number of injections for research subjects. The studies proposed in this application fall within these guidelines.

A 5 mCi (185 MBq) injection of Ga-68 DOTATATE results in a whole-body effective dose equivalent of 0.48 rem (4.8 mSv) and critical organ absorbed doses of 2.3 rad (23.1 mGy) to the urinary bladder wall, 1.7 rad (17.0 mGy) to the kidneys, and 5.2 rad (52.2 mGy) to the spleen (45).

The level of radiation for the PET scan is the same as received in widely used diagnostic studies such as the currently used 18F-FDG and is equal to or less than 80 percent of the amount allowed a radiation worker in a year (5 rem). The calculated whole body exposure to the individual will be less than 0.5 rem for each PET scan (1.05 total). Radiation exposure for the transmission images on the GE690 PET-CT (with which this study would be conducted) is 0.55 rem (5.5 mSv).

I. References and appendices

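### Section H says the study meets its quoted radiation limits, but its own spleen dose at the C.2 activity is 4.4% above the single-injection organ limit

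*Combined protocol and SAP*

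**What the plan says.** Section H takes its dose limits from a federal rule that it cites. For the whole body these are 30 mSv per injection and 50 mSv per year. For a single organ they are 50 mSv per injection ("A single organ cannot receive more than 5 rem (50mSv) in a single injection") and 150 mSv per year. It warns that "Often the limit for an individual organ dose is reached before the limit established for the whole-body", and concludes: "The studies proposed in this application fall within these guidelines".

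The next paragraph gives reference doses for 5 mCi (185 MBq): 4.8 mSv to the whole body, 23.1 mGy to the bladder wall, 17.0 mGy to the kidneys, and "5.2 rad (52.2 mGy) to the spleen (45"). Section H also puts whole-body exposure below 0.5 rem for each PET scan, gives 5.5 mSv for the CT component, and limits patients to one tracer scan a year ("The maximum number of PET studies a patient will receive in one year is 1 Ga-68 DOTATATE study").

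Activity is stated in two places. C.2, the imaging procedure, gives 5 mCi twice, once as approximately 5 mCi (185 MBq), with no weight term. C.1, the kit-preparation text, gives a recommended amount of "2 MBq/kg of body weight (0.054 mCi/kg) up to 200 MBq (5.4 mCi"). No text links the two.

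**The concern.** The compliance sentence is an assurance about safety, and the figure that contradicts it is in the paragraph that follows. The spleen has the highest organ dose listed, so it is the organ that decides whether the single-injection limit is met. Section H has just told the reader that organ limits are often the binding ones. It also says that "The study will be approved by not only the Emory IRB but also the Radiation Safety Committee", so these bodies may rely on the sentence.

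What is at stake is the accuracy of the assurance and, if the limit applies to this study, whether the planned activity respects it. The second activity statement in C.1 is a lesser matter. It leaves open which activity the dosimetry should describe.

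**Working it through.** **Inputs.** All are from the protocol: the limits, organ doses, whole-body dose and CT dose from Section H; 5 mCi (185 MBq) from C.2 and Section H; 2 MBq/kg with a 200 MBq cap from C.1.

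**Assumptions.** Absorbed dose is read as equivalent dose at 1 mGy = 1 mSv (weighting factor 1 for positron and photon emission), and dose is taken as proportional to activity. The protocol states neither.

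**1. Units.** 5 × 37 = 185 MBq, so C.2 and the Section H dosimetry describe the same activity. 5.2 rad is 52 mGy, which agrees with 52.2 mGy after rounding.

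**2. Each quoted limit at 185 MBq.**

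| Quantity | Dose | Limit | Dose / limit |
|---|---|---|---|
| Whole body, one injection | 4.8 mSv | 30 mSv | 16.0% |
| Whole body, annual, CT included | 4.8 + 5.5 = 10.3 mSv | 50 mSv | 20.6% |
| Bladder wall, one injection | 23.1 mGy | 50 mSv | 46.2% |
| Kidneys, one injection | 17.0 mGy | 50 mSv | 34.0% |
| Spleen, one injection | 52.2 mGy | 50 mSv | **104.4%** |
| Spleen, annual (one scan) | 52.2 mGy | 150 mSv | 34.8% |

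Only the single-injection spleen comparison fails: 52.2 − 50 = 2.2, and 2.2/50 = 4.4%. With the rounded figures, 5.2 rad against 5 rem is 4.0% over. The protocol gives no CT dose to the spleen, so none is included; it could only add.

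**3. How far the conversion matters.** The spleen figure would come down to the limit only with a factor of 50/52.2 = 0.958 mSv per mGy or less. The protocol offers no such factor.

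**4. Activity at which the reference spleen dose equals the limit.** 52.2/185 = 0.2822 mGy/MBq, and 50/0.2822 = 177.2 MBq (4.79 mCi). That is 1 − 177.2/185 = 4.2% below the C.2 activity. At 177 MBq the dose is 177 × 0.2822 = 49.9 mGy, a margin of 0.1 mGy.

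**5. C.1 against C.2.** 185/2 = 92.5 kg is the only body weight at which they agree. At 70 kg, C.1 gives 2 × 70 = 140 MBq, and C.2 is 185/140 − 1 = 32% higher. At 100 kg or more, C.1 gives 200 MBq, and C.2 is 7.5% lower (185/200 = 0.925).

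**6. The 200 MBq cap against Section H.** Whole body: 0.48 × 200/185 = 0.519 rem, above the stated bound of 0.5 rem per PET scan. Reference spleen dose: 200 × 0.2822 = 56.4 mGy, or 12.9% over 50.

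**The case against.** The strongest reply is that very little is at issue. The excess is 2.2 mGy on one reference value. C.2 says approximately 5 mCi, and about 4% less activity removes the excess. With one scan a year, the spleen is far below the quoted annual limit. Nothing is hidden either, since a committee reading Section H sees the limit and the dose almost side by side. All of this is fair and sets the weight of the point, but it does not make the compliance sentence true. Staying under the limit would mean dosing below the stated target.

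A reader might infer that the study breaches federal dose limits. The documents do not support that. Section B describes the approved tracer as an "off-label probe for somatostatin receptors", and nothing in the protocol settles whether the cited rule governs such use.

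A reader might also turn the arithmetic into patient-level claims, for instance that under C.1 every man above a certain weight exceeds the limit. That would apply one reference coefficient at all body weights. The protocol gives neither a coefficient by weight nor any spread between patients, so the figures in steps 4 and 6 describe the reference value only.

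Finally, the C.1 and C.2 statements might be read as leaving the dose undefined. That overstates it. C.1 gives a recommendation within preparation text that follows the prescribing information, while C.2 is the procedure, and Section H uses the C.2 activity. C.2 most likely governs, and the protocol needs only to say so.

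**Conclusion.** The point holds as an internal contradiction in Section H: wrong as written, minor in dose, and worth correcting because it is a safety statement that is cheap to put right. At the C.2 activity the protocol's own reference spleen dose is 104.4% of the single-injection organ limit that it quotes and says it meets. This rests on 1 mGy = 1 mSv and on the reference value as printed. The other quoted limits are met on the figures given. Whether the limit binds this study is a question for the investigators to answer in the text. The C.1 and C.2 mismatch is real but secondary.

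**What to change.** 1. Replace the compliance sentence in Section H with: *At 185 MBq the reference spleen dose (52.2 mGy) exceeds the 50 mSv single-injection organ limit quoted above; the other quoted limits are met.* Follow it with a statement of whether that limit applies to this study and why, and give the mGy-to-mSv conversion used.
2. Notify the Radiation Safety Committee of the correction.
3. If the limit does apply, lower the target activity far enough below 177 MBq to leave a real margin. A target of 177 MBq itself leaves 0.1 mGy, which means little when dosing is approximate. As an illustration only, 160 MBq gives 160 × 0.2822 = 45.1 mGy.
4. State in C.1 that the C.2 activity (about 5 mCi, 185 MBq maximum) governs in place of the recommended 2 MBq/kg up to 200 MBq. This also keeps the 0.5 rem statement true. If step 3 lowers the target, carry the new figure through C.1, C.2 and Section H.

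Steps 1, 2 and 4 cost a short wording amendment and a note to the committee, plus care that measured doses stay at or below 185 MBq. Step 3 costs counts in proportion to the reduction: in the illustration, 1 − 160/185 = 13.5% fewer at the same acquisition time.
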